10.7. Appendix 7: Kidney Safety: Monitoring Guidelines

10.7.1. Laboratory Assessment of Change in Kidney Function and Detection of Kidney Injury

Standard kidney safety monitoring requires assessment of baseline and postbaseline Screat measurement to estimate kidney function [Screat-based eGFR] or creatinine clearance [eCrCl]. Obtaining Screening or Baseline Scys and postbaseline reflex Scys (if confirmed Screat increase ≥ 0.3 mg/dL) makes it feasible to distinguish AKI from DICI. If Screat increase is confirmed after baseline, then reflex measurement of Scys is indicated

ADULTS: Currently, 2021 CKD-EPI eGFR equations (Screat only-based and combined Screat plus Scys-based) are valid for use in adults only. At baseline Screat and Scys values are needed to calculate 2021 CKD-EPI eGFR by Screat only-based equation (see Table 10.7.2.1) and by combined Screat plus Scys-based equation. When post-baseline Screat increase ≥ 0.3 mg/dL is confirmed, then reflex Scys measurement is needed to enable post-baseline comparison of eGFR changes (Screat only-based eGFR and combined Screat plus Scys eGFR).

10.7.2. Age-Specific Kidney Function Calculation Recommendations

10.7.2.1. Adults (18 Years and Above)—2021 CKD-EPI Equations

eGFR (mL/min/1.73m²)²³

2021 CKD-EPI Screat Only	Screat (mg/dL)	Scys (mg/L)	Recommended eGFR Equation
Female	if ≤ 0.7	NA	$eGFR = 143 \times (Screat/0.7)^{-0.241} \times (0.9938)^{Age}$
Female	if > 0.7	NA	$eGFR = 143 \times (Screat/0.7)^{-1.200} \times (0.9938)^{Age}$
Male	if ≤ 0.9	NA	$eGFR = 142 \times (Screat/0.9)^{-0.302} \times (0.9938)^{Age}$
Male	if > 0.9	NA	$eGFR = 142 \times (Screat/0.9)^{-1.200} \times (0.9938)^{Age}$
2021 CKD-EPI Screat-Scys Combined	Screat (mg/dL)	Scys (mg/L)	Recommended eGFR Equation
Female	if ≤ 0.7	if ≤ 0.8	$eGFR = 130 \times (Screat/0.7)^{-0.219} \times (Scys/0.8)^{-0.323} \times (0.9961)^{Age}$
Female	if ≤ 0.7	if > 0.8	$eGFR = 130 \times (Screat/0.7)^{-0.219} \times (Scys/0.8)^{-0.778} \times (0.9961)^{Age}$
Female	if > 0.7	if ≤ 0.8	$eGFR = 130 \times (Screat/0.7)^{-0.544} \times (Scys/0.8)^{-0.323} \times (0.9961)^{Age}$
Female	if > 0.7	if > 0.8	$eGFR = 130 \times (Screat/0.7)^{-0.544} \times (Scys/0.8)^{-0.778} \times (0.9961)^{Age}$
Male	if ≤ 0.9	if ≤ 0.8	$eGFR = 135 \times (Screat/0.9)^{-0.144} \times (Scys/0.8)^{-0.323} \times (0.9961)^{Age}$
Male	if ≤ 0.9	if > 0.8	$eGFR = 135 \times (Screat/0.9)^{-0.144} \times (Scys/0.8)^{-0.778} \times (0.9961)^{Age}$
Male	if > 0.9	if ≤ 0.8	$eGFR = 135 \times (Screat/0.9)^{-0.544} \times (Scys/0.8)^{-0.323} \times (0.9961)^{Age}$
Male	if > 0.9	if > 0.8	$eGFR = 135 \times (Screat/0.9)^{-0.544} \times (Scys/0.8)^{-0.778} \times (0.9961)^{Age}$

10.7.3. Kidney Function Calculation Tools

The sponsor has provided the following resources to investigational sites when required to calculate age-specific kidney function at Screening, Baseline, and post-Baseline visits. Site calculations of kidney function can be performed manually, using the age appropriate formulae (see [Section 10.7.2](#)) and can use recommended online kidney function calculators to reduce the likelihood of a calculation error.

The United States National Kidney Foundation Online Calculators.

- Adults (18 years and above) - 2021 CKD-EPI Creatinine Online Calculator (eGFR):
https://www.kidney.org/professionals/KDOQI/gfr_calculator

Investigational sites are responsible to ensure that the accurate age-specific equation is selected and that the correct units for serum creatinine (mg/dL only), serum cystatin C (mg/L only), total body weight (kg only), and age (years). Investigators are expected to (i) review and confirm correctness of the kidney function calculation results and (ii) evaluate the calculated value within the context of historical information available to them in the participant's medical record. Investigators are responsible for the clinical oversight of the participant eligibility process, kidney function calculation, and dose selection and adjustments per study protocol. Investigators are encouraged to direct questions or uncertainties regarding kidney function and dosing to the Pfizer Clinical Team and Medical Monitor, if needed.

10.7.4. Adverse Event Grading for Kidney Safety Laboratory Abnormalities

AE grading for decline in kidney function (ie, eGFR or eCrCl) will be according to Kidney Disease: Improving Global Outcomes (KDIGO) criteria for both pediatric and adult participants.

<https://kdigo.org/guidelines/>

KDIGO criteria grade (G)	Study Population	G1	G2	G3	G4	G5
Decreased Kidney Function due to either Acute or Chronic Kidney Injury	Adult participants eGFR (mL/min/1.73m ²)	≥90	≥60 to 89	30 to 59	15 to 29	<15

KDIGO albuminuria (A) criteria	A1	A2	A3
Albumin-to-creatinine ratio (ACR)	<30 mg/g OR <3 mg/mmol	30 to 300 mg/g OR 3 to 30 mg/mmol	>300 mg/g OR >30 mg/mmol

10.8. Appendix 8: ECG Findings of Potential Clinical Concern

ECG Findings That May Qualify as AEs

Marked sinus bradycardia (rate <40 bpm) lasting minutes.New PR interval prolongation >280 ms.New prolongation of QTcF to >480 ms (absolute).New prolongation of QTcF by >60 ms from baseline.New-onset atrial flutter or fibrillation, with controlled ventricular response rate: ie, rate <120 bpm.New-onset type I second-degree (Wenckebach) AV block of >30-second duration.Frequent PVCs, triplets, or short intervals (<30 seconds) of consecutive ventricular complexes.
ECG Findings That May Qualify as SAEs

QTcF prolongation >500 ms.Absolute value of QTcF > 450 ms AND QTcF change from baseline >60 ms.New ST-T changes suggestive of myocardial ischemia.New-onset LBBB (QRS complex >120 ms).New-onset right bundle branch block (QRS complex >120 ms).Symptomatic bradycardia.Asystole
In awake, symptom-free participants in sinus rhythm, with documented asystolic pauses ≥ 3 seconds or any escape rate <40 bpm, or with an escape rhythm that is below the AV node;In awake, symptom-free participants with atrial fibrillation and bradycardia with 1 or more asystolic pauses of at least 5 seconds or longer.Atrial flutter or fibrillation, with rapid ventricular response rate: rapid = rate >120 bpm.

- Sustained supraventricular tachycardia (rate >120 bpm) (“sustained” = short duration with relevant symptoms or lasting >1 minute).
- Ventricular rhythms >30 seconds’ duration, including idioventricular rhythm (HR <40 bpm), accelerated idioventricular rhythm (HR >40 bpm to <100 bpm), and monomorphic/polymorphic ventricular tachycardia (HR >100 bpm [such as torsades de pointes]).
- Type II second-degree (Mobitz II) AV block.
- Complete (third-degree) heart block.

ECG Findings That Qualify as SAEs

- Change in pattern suggestive of new myocardial infarction.
- Sustained ventricular tachyarrhythmias (>30-seconds duration).
- Second- or third-degree AV block requiring pacemaker placement.
- Asystolic pauses requiring pacemaker placement.
- Atrial flutter or fibrillation with rapid ventricular response requiring cardioversion.
- Ventricular fibrillation/flutter.
- At the discretion of the investigator, any arrhythmia classified as an adverse experience.

[figure not shown]
The major events of potential clinical concern listed above are recommended as “alerts” or notifications from the core ECG laboratory to the investigator and Pfizer study team, and not to be considered as all-inclusive of what is to be reported as AEs/SAEs.

10.9. Appendix 9: Prohibited Concomitant Medications That May Result in DDI

CCI [REDACTED]. Therefore, as outlined in [Section 5.2](#) and [Section 6.9](#), use of prescription or nonprescription drugs and dietary and herbal supplements that are CCI [REDACTED] are prohibited within 14 days plus 5 half-lives prior to the first dose of study intervention.

A non-exhaustive list of CCI [REDACTED] is below. Because this is not an all-inclusive list, site staff should consult with the sponsor or designee with any questions regarding potential DDI. The Pfizer study team is to be notified of any prohibited medications taken during the study.

CCI [REDACTED]

CCI

In a situation where appropriate medical care of a participant requires the use of a prohibited CCI [REDACTED]
CCI [REDACTED]: These medications are not permitted in the study except in emergency situations requiring no more than one day of administration. Topical application of antimicrobial and antifungal medications is permitted.

This list of drugs prohibited for potential DDI concerns may be revised during the course of the study with written notification from sponsor, to include or exclude specific drugs or drug categories for various reasons (eg, emerging DDI results for the IMP, availability of new information in literature on the DDI potential of other drugs), if the overall benefit:risk assessment is not impacted or if the changes do not significantly impact the safety of participants or the scientific value of the trial.

10.10. Appendix 10: Abbreviations

The following is a list of abbreviations that may be used in the protocol.

Abbreviation	Term
A1 to A3	albuminuria (KDIGO albuminuria severity standardization)
Abs	absolute
ACC	acetyl-CoA carboxylase
ADL	activity/activities of daily living
ADP	adenosine diphosphate
AE	adverse event
AKI	acute kidney injury
ALT	alanine aminotransferase
AMP	adenosine monophosphate
AMPK	AMP-activated protein kinase
AMPK γ 3	5'-AMP-activated protein kinase subunit gamma-3
ANOVA	analysis of variance
AST	aspartate aminotransferase
ATP	Adenosine triphosphate
AUC	area under the concentration-time curve
AUC ₂₄	area under the concentration-time curve from time 0 to 24 hours
AUC _{inf}	area under the concentration-time curve from time 0 to infinity
AUC _{inf(dn)}	dose normalized AUC _{inf}
AUC _{last}	area under the concentration-time curve from 0 to time of last measurable concentration
AUC _{last(dn)}	dose normalized AUC _{last}
AV	atrioventricular
AxMP	auxiliary medicinal product
BBS	Biospecimen Banking System
CCI	
BMI	body mass index
BP	blood pressure
bpm	beats per minute
C _{eff}	Efficacious concentration
CFR	Code of Federal Regulations
CIOMS	Council for International Organizations of Medical Sciences
CK	creatine kinase
CKD-EPI	chronic kidney disease epidemiology
CL/F	apparent clearance
C _{last}	the predicted plasma concentration at the last quantifiable timepoint estimated from the log-linear regression analysis
CCI	
C _{max}	maximum observed concentration
C _{max(dn)}	dose-normalized C _{max}

Abbreviation	Term
CNS	central nervous system
CO ₂	carbon dioxide (bicarbonate)
COVID-19	coronavirus disease 2019
CCI	
CRF	case report form
CRO	contract research organization
CRU	clinical research unit
CSR	Clinical Study Report
CT	clinical trial
CTIS	Clinical Trial Information System
CCI	
DCT	data collection tool
DDI	drug-drug interaction
DICI	drug-induced creatinine increase
DIKI	drug-induced kidney injury
DILI	drug-induced liver injury
DIO	diet induced obese
DNA	deoxyribonucleic acid
EC	ethics committee
ECC	emergency contact card
ECG	electrocardiogram or electrocardiography
eCrCl	estimated creatinine clearance
eCRF	electronic case report form
EDB	exposure during breastfeeding
E-DMC	External Data Monitoring Committee
EDP	exposure during pregnancy
EDR	extemporaneous dispensing record
eGFR	estimated glomerular filtration rate
eICD	electronic informed consent document
EMA	European Medicines Agency
eSAE	electronic serious adverse event
ET	early termination
EU	European Union
EudraCT	European Union Drug Regulating Authorities Clinical Trials (European Clinical Trials Database)
FDA	Food and Drug Administration
FIH	first in human
CCI	
FSH	follicle-stimulating hormone
f _{u,p}	fraction unbound in plasma
GCP	Good Clinical Practice
GGT	gamma-glutamyl transferase
GLP	Good Laboratory Practice

Abbreviation	Term
Hb	hemoglobin
HBcAb	hepatitis B core antibody
HBsAb	hepatitis B surface antibody
HBsAg	hepatitis B surface antigen
HCVAb	hepatitis C antibody
HEK	human embryonic kidney
HFpEF	heart failure with preserved ejection fraction
HIV	human immunodeficiency virus
hKI	humanized knock-in
HR	heart rate
HRT	hormone replacement therapy
IB	Investigator's Brochure
CCI	
ICD	informed consent document
ICH	International Council for Harmonisation of Technical Requirements for Pharmaceuticals for Human Use
ID	identification
IMP	investigational medicinal product
IND	Investigational New Drug
INR	international normalized ratio
IPAL	Investigational Product Accountability Log
IRB	Institutional Review Board
IV	Intravenous(ly)
K ₂ EDTA	dipotassium ethylenediaminetetraacetic acid
KDIGO	Kidney Disease Improving Global Outcomes
KDOQI	Kidney Disease Outcomes Quality Initiative
kel	first-order elimination rate constant
KI	knockin
KO	knockout
LBBB	left bundle branch block
LFT	liver function test
CCI	
MCH	mean corpuscular hemoglobin
MCHC	mean corpuscular hemoglobin concentration
MCV	mean corpuscular volume
CCI	
MQI	medically qualified individual
NA	not applicable
NC	not calculated
ND	not done
NIMP	noninvestigational medicinal product
NOAEL	no observed adverse effect level
NOEL	no observed effect level

Abbreviation	Term
NS	no sample
CCI	
OCT	organic cation transporter
CCI	
Pbo	placebo
PD	pharmacodynamic(s)
PE	Physical Examination
CCI	
PGx	pharmacogenomic(s)
PI	principal investigator
PK	pharmacokinetic(s)
PO	by mouth
PR	pulse rate
PSSA	Pfizer's Serious Adverse Event Submission Assistant
PT	prothrombin time
PVC	premature ventricular contraction/complex
CCI	
QTc	corrected QT interval
QTcF	QTc corrected using Fridericia's formula
qual	qualitative
RBC	red blood cell
RNA	ribonucleic acid
RR	respiratory rate
SAE	serious adverse event
SAP	Statistical Analysis Plan
SAR	Serious Adverse Reaction
SC	subcutaneous
Screat	serum creatinine
Scys	serum cystatin C
SDD	spray dried dispersion
CCI	
SoA	schedule of activities
SOP	standard operating procedure
SRSD	Single Reference Safety Document
SUSAR	Suspected Unexpected Serious Adverse Reaction
$t_{\frac{1}{2}}$	terminal phase half-life
T bili	total bilirubin
THC	tetrahydrocannabinol
T_{max}	time to reach C_{max}
UACR	urine albumin/creatinine ratio
UGT	uridine 5'-diphospho-glucuronosyltransferase
ULN	upper limit of normal
US	United States

Abbreviation	Term
UTI	urinary tract infection
VO ₂	oxygen consumption
CCI	
Vz/F	apparent volume of distribution for extravascular dosing
WBC	white blood cell
WOCBP	woman/women of childbearing potential

1. VERSION HISTORY

Table 1. Summary of Changes

Version/ Date	Associated Protocol Amendment	Rationale	Specific Changes
1 13 Jul 2023	Final Protocol Amendment 1 07 Jun 2023	N/A	N/A
2 21 Mar 2024	Final Protocol Amendment 1 07 Jun 2023 Protocol Administrative Change Letter (PACL) for Amendment 1 14 Dec 2023	Food effect added to SDD formulation	
 Throughout: General updates to add the evaluation of food effect in SDD formulation per PACL 14-Dec-2023. Section 2.2: tertiary objective of food effect updated to match PACL. Typo of “secondary” corrected. Section 3.2: footnote of Table 2 updated. Section 6.2: analysis of food effect in SDD formulation added. Appendix 3: abbreviation of PACL added.

2. INTRODUCTION

This study will be the first time that PF-07293893 is administered to humans. The purpose of the study is to evaluate the safety, tolerability, and plasma pharmacokinetics (PK) of PF-07293893 following administration of escalating single oral doses to healthy adult participants.

This statistical analysis plan (SAP) provides the detailed methodology for summary and statistical analyses of the data collected in Study C5171001. This document may modify the plans outlined in the protocol; however, any major modifications of the primary endpoint definition or its analysis will also be reflected in a protocol amendment.

2.1. Modifications to the Analysis Plan Described in the Protocol

No modification.

2.2. Study Objectives, Endpoints, and Estimands

Type	Objective	Endpoint
	Primary	Primary
Safety Section 6.1	
 To evaluate the safety and tolerability of single ascending doses of PF-07293893 administered orally to healthy adult participants. 	
 Assessment of adverse events, clinical safety laboratory tests, vital signs, continuous cardiac monitoring, 12-lead electrocardiograms, physical examinations and neurological examinations.
	Secondary	Secondary
PK Section 6.2	
 To evaluate the PK of PF-07293893 following single doses of PF-07293893 administered orally to healthy adult participants. 	
 PK parameters derived from plasma PF-07293893 concentrations: C_{max}, T_{max}, AUC_{last}, and if data permit, AUC_{inf}, and $t_{1/2}$.
	Tertiary/Exploratory	Tertiary/Exploratory
PK Section 6.3.1	
 To evaluate additional PK parameters of PF-07293893 following single doses of PF-07293893 administered orally to healthy adult participants. 	
 Additional PK parameters derived from plasma PF-07293893 concentrations: $C_{max}(dn)$, $AUC_{last}(dn)$ and if data permit, $AUC_{inf}(dn)$, CL/F and V_z/F.
PK Section 6.3.2	
 To evaluate the PK of PF-07293893 following single dose(s) of a crystalline and SDD form of PF-07293893 in fasted and/or fed state, if conducted. 	
 PK parameters derived from plasma PF-07293893 concentrations: C_{max}, T_{max}, AUC_{last}, and if data permit, AUC_{inf}, and $t_{1/2}$.
Biomarker Section 6.3.3	
 To evaluate the effects of single ascending doses of PF-07293893 on biomarker(s) of transporter activity, if feasible & analyzed. 	
 For each biomarker (as applicable): AUC_{24} and C_{max}

There are no estimands for this study.

[figure not shown]
2.3. Study Design

This is a randomized, investigator- and participant-blind, sponsor-open, placebo-controlled, first-in-human, single ascending oral dose, 4-period, crossover study of PF-07293893 administered to healthy adult participants. Approximately 24 healthy adult participants (up to 3 cohorts of approximately 8 participants each) will be enrolled in this study. The first 2 cohorts are planned, and the third cohort is optional. In each period, participants will be randomized to either PF-07293893 or placebo in a ratio of 3:1. Each participant is planned to undergo up to 4 treatment periods receiving up to 4 doses of PF-07293893 and up to 2 doses of placebo.

Precautionary sentinel dosing will be used in any period evaluating escalating doses of PF-07293893 and may be omitted for periods when repeating a dose level or administering a lower dose level than previously evaluated. For periods with sentinel dosing, two participants (1 receiving PF-07293893 and 1 receiving placebo) will be dosed initially before the remaining participants of that period are dosed. Safety and tolerability data through at least 24 hours post-dose for the sentinel participants will be reviewed prior to dosing the remaining participants of that period.

The study design schema is shown below in Figure 1.

Figure 1. Study Design Schema^{a,b,c}

- a. Doses shown for each cohort except the starting dose in Cohort 1 are planned doses and may be modified based on emerging data from previous cohorts. Similarly, assignment to study intervention may be modified. n represents number of participants.
- b. SDD extemporaneous prep will be used for dose escalation in this study. PK for crystalline formulation (fasted/fed) may be studied in remaining periods of Cohort 2 and/or optional Cohort 3 when it becomes available.
- c. Precautionary sentinel dosing will be used in any period evaluating escalating doses of PF-07293893. For such periods, 2 participants (1 receiving PF-07293893 and 1 receiving placebo) will be dosed initially before the remaining participants of that period are dosed. Safety and tolerability data through at least 24 hours post-dose for the sentinel participants will be reviewed prior to dosing the remaining participants of that period. Sentinel dosing may be omitted when repeating a dose level or administering a lower dose level than previously evaluated.

3. ENDPOINTS AND BASELINE VARIABLES: DEFINITIONS AND CONVENTIONS

3.1. Primary Endpoint(s)

Primary endpoints include assessment of adverse events (AEs), clinical safety laboratory tests, vital signs, continuous cardiac monitoring, 12-lead electrocardiograms (ECG), physical examinations and neurological examinations during the entire study, by period.

Any events occurring following start of study intervention (ie, treatment with PF-07293893 or placebo) will be counted as treatment emergent.

Events that occur in a non-treatment period (eg, washout or follow-up) will be counted as treatment emergent and attributed to the most recent treatment taken.

A 3-tier approach for summarizing adverse events will not be used due to the low number of participants planned to be recruited.

The following data are considered in standard safety summaries (see protocol for collection days and list of parameters):

- adverse events,
- laboratory data (except data from screening visit),
- vital signs data,
- ECG results,
- cardiac monitoring,
- physical examinations,
- neurological examinations.

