1.3. Schedule of Activities

The SoA table provides an overview of the protocol visits and procedures. Refer to the **STUDY ASSESSMENTS AND PROCEDURES** section of the protocol for detailed information on each procedure and assessment required for compliance with the protocol.

The investigator may schedule visits (unplanned visits) in addition to those listed in the SoA table, in order to conduct evaluations or assessments required to protect the well-being of the participant.

Table 1. Study Schedule of Assessment

Visit Identifier Abbreviations used in this table may be found in Appendix 10 .	Screen	Period 1 to Period 4					F/U		ET	Notes
Days Relative to Day 1	Day -28 to Day -2	Day -1	Day 1	Day 2	Day 3	Day 4	Visit: Day 8±1	Contact: Day 29-36		
• All screening should be done \leq28 days before the first dose.• Day relative to start of study intervention (Day 1).• Day 1 activities at time=0 hours are prior to the dose, except for study intervention administration.• On-site follow-up visit to occur on Day 8±1 after the final dose of study intervention.• Follow-up may occur via telephone contact and must occur 28 to 35 days after administration of the final dose of study intervention.
Hours After Dose		0	24	36	48	72				
Outpatient visit	X						X			
Informed consent	X									
• Informed consent should be obtained prior to undergoing any study-specific procedures. See Section 10.1.3 for additional information.
CRU confinement		X	→	→	→	→	X			
• Admission on Day -1 in Period 1 of each cohort.
Inclusion/exclusion criteria	X	X								
• Period 1 only. Review any changes from Screening.
Medical/medication history	X	X								
• Period 1 only. Review any changes from Screening.
History of alcohol, tobacco, and illegal drug use	X	X								
• Period 1 only. Review any changes from Screening.
Review concomitant treatments	X	→	→	→	→	→	→	X	X	
• See Section 6.9 for additional information.

Table 1. Study Schedule of Assessment

Visit Identifier Abbreviations used in this table may be found in Appendix 10 .	Screen	Period 1 to Period 4					F/U		ET	Notes
		Day -1	Day 1	Day 2	Day 3	Day 4	Visit: Day 8±1	Contact: Day 29-36		

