Screening activities will be completed over the 28 days prior to randomization in Period 1. Participants confirming eligibility according to [Section 5](#) will be admitted to the CRU on Day -1 in Period 1 for each cohort. For each period in this study, on Day 1, following ≥ 10 hour overnight fast, participants will receive a single oral dose of PF-07293893 or placebo. Participants will be discharged on Day 4, following completion of all scheduled assessments (approximately 72 hours post-dose). Participants may be asked to remain in the CRU after completion of Day 4 activities at the discretion of the investigator or if safety, tolerability, or PK data dictate the need to prolong confinement in the CRU. In each cohort, a washout interval of at least 7 days will be introduced between subsequent doses. During the washout interval, emerging 24-hour PK and 72-hour safety data will be reviewed and the next dose will be determined. An on-site follow-up visit will occur on Day 8 ± 1 after the final dose. The follow-up contact may occur via telephone contact and must occur 28–35 days after administration of the final dose of study intervention. The total planned duration of participation from the screening visit to the telephone follow-up contact will be approximately 14 weeks.

Based on the review of emerging safety, tolerability, and PK data in Cohorts 1 and 2, the remaining periods of Cohort 2 and/or an optional third cohort enrolling approximately 8 participants (crossover, placebo controlled design) may be used to explore additional doses, to repeat a dose, or to evaluate effect of crystalline form on PF-07293893 PK in fasted and/or fed state.

Dosing will occur in the fasted state for all periods, except if an optional exploratory assessment of the effect of food on crystalline PF-07293893 PK is conducted. The actual dose level for the assessment of food effect will be selected based on emerging safety, tolerability, and PK data but will be expected to achieve projected therapeutic exposures ([Section 4.3.2](#)).

If a participant drops out before completing all study periods within a cohort, or withdraws for a reason unrelated to safety, the participant may be replaced at the discretion of the investigator and sponsor. The replacement participant(s) may or may not be required to complete all periods of the cohort in which they are participating at the discretion of the investigator and sponsor.

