8.4.1. Time Period and Frequency for Collecting AE and SAE Information

The time period for actively eliciting and collecting AEs and SAEs (“active collection period”) for each participant begins from the time the participant provides informed consent, which is obtained before undergoing any study-related procedure and/or receiving study intervention), through and including a minimum of 28 calendar days, except as indicated below, after the last administration of the study intervention.

Follow-up by the investigator continues throughout the active collection period and until the AE or SAE or its sequelae resolve or stabilize at a level acceptable to the investigator.

When a clinically important AE remains ongoing at the end of the active collection period, follow-up by the investigator continues until the AE or SAE or its sequelae resolve or stabilize at a level acceptable to the investigator and Pfizer concurs with that assessment.

For participants who are screen failures, the active collection period ends when screen failure status is determined.

If the participant withdraws from the study and also withdraws consent for the collection of future information, the active collection period ends when consent is withdrawn.

If a participant permanently discontinues or temporarily discontinues study intervention because of an AE or SAE, the AE or SAE must be recorded on the CRF and the SAE reported using the CT SAE Report Form.

Investigators are not obligated to actively seek information on AEs or SAEs after the participant has concluded study participation. However, if the investigator learns of any SAE, including a death, at any time after a participant has concluded study participation, and they consider the event to be reasonably related to the study intervention, the investigator must promptly report the SAE to Pfizer using the CT SAE Report Form/ PSSA.

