3.1.1. Adverse Events

An adverse event is considered a Treatment-Emergent Adverse Event (TEAE) if the event started during the effective duration of treatment. All events that start on or after the first dose of study intervention, but before the end of the study will be flagged as TEAEs. The algorithm will not consider any events that started prior to the first dose date.

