6.1.1. Adverse Events

Adverse events will be listed and summarized by dose and treatment (if applicable) and overall, in accordance with sponsor reporting standards using the safety analysis set defined in Section 4.

The AEs will be presented sorted in descending frequency based on the overall number of AEs (by preferred term or system order class as appropriate) across treatments.

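### The adverse-event attribution window has no day limit, so each participant's last treatment is observed about 2 to 3 times as long as earlier ones and the by-dose adverse-event columns are not comparable

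*SAP*

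**What the plan says.** The attribution rule is in SAP 3.1: events arising in a non-treatment period such as washout or follow-up "will be counted as treatment emergent and attributed to the most recent treatment taken". SAP 3.1.1 sets the outer limits: "All events that start on or after the first dose of study intervention, but before the end of the study will be flagged as TEAEs". That section also mentions an effective duration of treatment but gives it no number of days.

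The timing comes from the protocol:

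- **Between doses.** Section 4.1 states that "a washout interval of at least 7 days will be introduced between subsequent doses".
- **After the last dose.** Section 8.4.1 has AEs actively collected "through and including a minimum of 28 calendar days" after the last administration. The Schedule of Activities adds a follow-up contact that "must occur 28 to 35 days after administration of the final dose of study intervention".
- **Overall.** Section 4.1 gives a total participation of approximately 14 weeks, from screening to the telephone contact.

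For reporting, SAP 6.1.1 says "Adverse events will be listed and summarized by dose and treatment (if applicable) and overall". SAP 5.2 uses a single placebo group pooled over the dose-escalation periods. SAP 6.5.3 marks study treatment exposure as not applicable. Neither document specifies a common post-dose window or an AE rate per unit of observation time.

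**The concern.** In a crossover with unequal follow-up after each treatment, a rule that assigns every event to the latest treatment gives the treatments unequal observation time. Here the inequality is built into the schedule: every period except a participant's last is cut off by the next dose, and the last runs to the follow-up contact. Minor events unrelated to drug, such as a cold or a headache at home, accumulate where the window is longest.

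Safety and tolerability by ascending dose is the primary objective. With about 6 active participants per dose, one or two background events change how a column looks. The result is a step at the last treatment of each cohort. If that treatment is the cohort's highest dose, the step resembles a dose effect. If it is a repeated dose, or a food or formulation period, the pattern is distorted in some other way.

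Placebo does not fully correct for this. In a complete cohort 6 of the 8 placebo administrations fall in Periods 1 to 3, so the pooled placebo column has on average a much shorter window than the last active treatment.

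**Working it through.** **1. The stated duration.** The inputs are up to 28 days of screening (Protocol 4.1: "Screening activities will be completed over the 28 days prior to randomization in Period 1"), three dosing intervals, and 28 to 35 days to the final contact.

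- At the 7-day minimum: 28 + 3×7 + 28 = 77 days (11 weeks), or 28 + 3×7 + 35 = 84 days (12 weeks).
- The stated 14 weeks is 98 days. The mean interval it implies is (98 − 28 − 28)/3 = 14 days, or (98 − 28 − 35)/3 = 11.7 days.

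The 14 weeks is thus compatible with the minimum interval but points to spacing of about 12 to 14 days. If screening takes less than 28 days of the 14 weeks, the implied intervals lengthen and the ratios below fall.

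**2. Window ratio, last treatment against an earlier one.**

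- Implied spacing: 28/14 = 2.0; 35/11.7 = 3.0.
- Minimum spacing: 28/7 = 4.0; 35/7 = 5.0.

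**3. Window ratio, last active treatment against pooled placebo.** With 2 placebo administrations in each of 4 periods, the mean placebo window is (6 × interval + 2 × follow-up)/8.

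| Interval / follow-up (days) | Mean placebo window (days) | Ratio |
|---|---|---|
| 14 / 28 | 17.5 | 1.6 |
| 11.7 / 35 | 17.5 | 2.0 |
| 7 / 28 | 12.25 | 2.3 |
| 7 / 35 | 14.0 | 2.5 |

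These ratios are per placebo administration. A participant who receives placebo twice contributes both windows, which narrows the contrast when participants are counted.

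**4. Effect on counts.** The documents give no background AE rate. Assume a constant rate r per participant-day, equal at every dose (no drug effect). The expected number of participants with at least one AE is 6 × (1 − exp(−r × days)).

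| r | 7 d | 11.7 d | 14 d | 28 d | 35 d |
|---|---|---|---|---|---|
| 0.005 | 0.21 | 0.34 | 0.41 | 0.78 | 0.96 |
| 0.01 | 0.41 | 0.66 | 0.78 | 1.47 | 1.77 |
| 0.02 | 0.78 | 1.25 | 1.47 | 2.57 | 3.02 |
| 0.03 | 1.14 | 1.77 | 2.06 | 3.41 | 3.90 |

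At 0.02 per day the consistent pairs are 1.5 against 2.6 (14 and 28 days) and 1.2 against 3.0 (11.7 and 35 days). At the 7-day minimum the pair is 0.8 against 2.6 to 3.0.

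**5. How often the last treatment would look worst by chance.** Take four treatments with binomial counts out of 6, treated as independent; this is an approximation, because the same participants recur across periods. For r from 0.005 to 0.03, the probability that the last treatment has strictly the highest count is:

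- equal 7-day windows: 11% to 15%;
- 14 against 28 days: 27% to 48%;
- 11.7 against 35 days: 37% to 69%;
- 7 against 28 days: 38% to 75%; 7 against 35 days: 45% to 84%.

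**6. Sensitivity to the constant rate.** Suppose instead 0.05 per day over 4 days of confinement and 0.005 per day afterwards (again an assumption). The cumulative hazard is 0.2 + 0.005 × (days − 4). The expected counts are then 1.3 against 1.6 of 6 (14 and 28 days) and 1.3 against 1.8 of 6 (11.7 and 35 days). The direction holds, but the gap is much smaller.

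**The case against.** **The direction is not fixed.** A reader might infer that the long window always falls on the highest dose and so creates a false dose trend. The documents do not support that. Protocol Table 3 lists six planned doses, while two cohorts of four periods give eight periods. Remaining Cohort 2 periods and Cohort 3 may repeat a dose, explore others, or test the crystalline form or food. If the six doses ran in sequence (an assumption, since the schema is not visible), Cohort 1 would end at 300 mg with the long window. The 750 and 1500 mg doses would sit in Cohort 2 Periods 1 and 2, with short windows if later periods follow. That would blunt a trend. This objection stands, and the point is limited to a step at each cohort's last treatment.

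**The 4-to-5-fold ratio is an extreme.** This also stands. It needs the minimum interval, and the stated duration points to 2 to 3.

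**Late capture is probably thinner.** Every period has the same confinement to Day 4. After the Day 8 visit, only the 28-to-35-day contact, which may be by telephone, is scheduled. This stands as a limit on size; step 6 shows its effect.

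**The consequences are contained.** No hypothesis test is planned, so type I error is not at issue. Escalation uses safety data through at least 72 hours plus cumulative data. Causality is assessed for every AE, and study day is counted within period, so a late event can be recognised in the listing. Last-period placebo participants also get the long window. All of this lowers the stakes, but it does not make the single-dose columns comparable.

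**The inclusive rule is defensible in a first-in-human study.** Agreed, and the fix leaves it in place. SAP 3.1 also refers to safety assessment by period, but that sets no window length. The sponsor reporting standards cited in SAP 6.1.1 cannot be seen; if they already impose a common window, the SAP should say so.

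**Conclusion.** The concern holds as a limitation of the by-dose AE table. Observation time differs by period: the last treatment has 28 to 35 days and earlier ones have a single dosing interval. The ratio is likely 2 to 3, reaches 4 to 5 at the 7-day minimum, and is about 1.6 to 2.5 against pooled placebo per administration. These ratios rest on stated timings, plus the reading that the 14 weeks includes a full screening period.

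The effect on counts rests on an assumed background rate. At a constant 0.02 per day the last treatment would show roughly one to two more participants out of 6 with an AE and no drug effect; under front-loaded capture the excess is about 0.3 to 0.5. Because the long window follows each participant's own last dose, it also reaches anyone who drops out after an earlier dose.

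The documents do not support a claim that a dose trend is bound to appear, or that dose escalation would be misled. The risk is that the final descriptive table is misread. It is a cheap improvement and worth making.

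**What to change.** Keep the attribution rule in SAP 3.1 and 3.1.1 and the all-events table. In SAP 6.1.1:

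- Add a treatment-emergent AE table by dose and treatment, restricted to onset within a common post-dose window in every period, including the last. Seven days is one example, because it is the longest window that the minimum interval guarantees for every dose.
- State that between-dose and dose-versus-placebo comparisons rest on this table.
- List later events with days since the last dose.

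The sponsor should justify the window length, since the projected half-life is not visible here. It should also note that SAP 6.1.2, 6.1.3 and 6.1.5 attribute pre-dose findings in the next period to the previous treatment, so with intervals longer than 7 days those findings and the windowed AE table would follow different rules.

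The cost is a few lines of SAP text and one extra table, with no change to trial conduct. The downside is that late-onset events, including any that begin just after the window closes, do not enter the between-dose comparison. They remain in the all-events table and the listing.
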